5.4. Randomisation

Following consent and baseline assessment, randomisation will be performed by a member of the trial team using a secure web-based system (REDCap). Participants will be randomised in a 1:1 ration to either the control (chest tube) or interventional (therapeutic thoracentesis) arm of the study. Randomisation will be randomly generated by the REDCap software to reduce selection bias. Randomisation will be stratified by size of the effusion on chest radiograph (>50% or <50% using visual estimation of the chest radiograph).

5.5. Blinding

It is impractical to conceal treatments from either patients or healthcare professionals. Therefore, the ACTion trial will be conducted unblinded.

5.6. Post randomisation

Control arm

Patients allocated to the control arm will have a chest tube inserted as per standard care. There should be minimal delay between randomisation and intervention in keeping with usual care for urgent pleural drainage.

The size of this tube is at the discretion of the treating physician and inserted using Seldinger technique after bedside ultrasound marking (as per local guidelines). The chest tube is attached to an underwater seal and drained according to the discretion of the treating physician.

Following insertion, any samples of pleural fluid that are required for clinical purposes should be taken from the chest tube e.g. microbiological analysis.

A post procedure chest radiograph should be performed after chest tube insertion.

Intervention arm

Patients who are allocated to the intervention arm will have therapeutic thoracentesis. Again, there should be minimal delay between randomisation and drainage. Separate procedural consent must be taken as per hospital policy. Drainage will be performed using a 6 or 8F French therapeutic thoracentesis kit using bedside ultrasound marking

Initially the effusion should be drained to dryness or until the patient develops symptoms associated with trapped lung (coughing or chest pain). Catheter blockages can be managed with a small volume flush of 10-100ml of normal saline (as would be done for chest tubes).

Following thoracentesis, samples of pleural fluid that are required for clinical purposes should be taken e.g. microbiological analysis.

A post procedure chest radiograph should be performed after each therapeutic thoracentesis.

5.7. Post procedure inpatient period

All patients

Whilst in hospital, all patients will have a clinical review on every working day. As a minimum a chest radiograph will be performed on Day 3 (+/- 1 day) and Day 7 (+/- 1 day), with additional as deemed necessary by the treating physician.

Blood tests should be performed on at least alternate days until day 7, and then at least weekly if the patient remains in hospital.

Thoracic ultrasounds should be performed on day 2 (the day after the first procedure), and then on days 3 (+/- 1 day) and 7 (+/- 1 day), with additional performed as deemed necessary by the treating physician.

Discharge from hospital is ultimately at the discretion of the treating physician. Numerous factors form the basis of this decision to the extent it becomes impossible to protocolise. It is assumed that

as part of good clinical care all aspects of a patient's condition will be assessed before discharge, including clinical status, outpatient follow up and social set up

Control groups

The timing for chest tube removal in the control group is at the discretion of the treating physician. If the chest tube is removed, the patient should have a chest radiograph afterwards.

Interventional group

There may be a requirement for patients to have further therapeutic aspirations if there is reaccumulation of infected pleural fluid. This is an anticipated drawback of this approach and will be explained to the patients as part of the randomisation process. The need for a timing of further procedures will be decided by the treating physician. It is advised they consider the following before making a decision

- clinical/biochemical factors (such as rising CRP/WBC, or fevers).
- Chest radiograph appearances suggesting persisting collections
- Pleural ultrasound appearances suggesting persisting collections as well as the amenability of these collections to drainage

5.8. Post procedure outpatient period

As dictated above patients will only be discharged if the treating clinician feels they are well enough and will be safe as an outpatient.

Patients in the control arm are likely only to be discharged if their pleural infection has resolved and chest tube has been removed. Patients in the interventional arm, given the nature of the drainage method, have the potential to be discharged before the pleural infection has completely resolved.

The treating physician will have the ability to ask patients from either arm of the study to return early outpatient clinics for repeat blood tests, clinical and radiological review, and even pleural procedures and intravenous antibiotics. It is likely that this service will be utilised more frequently for patients in the interventional arm. As an important part of the ACTion trial's health economic analysis, data will be collected from all patients about the requirement for outpatient hospital visits, primary care attendances, district nurse and social care visits, as burden on informal carers in their home.

5.9. Use of antibiotics

The choice (including type, route and course) of antibiotics is at the discretion of the treating physician. North Bristol NHS Trust has a policy covering empirical antibiotic choice in pleural infection. [name] (NBT Microbiology Consultant) is advising on this trial so if there are patients where different regimens are required, we will seek his advice.

5.10. Use of intrapleural therapies

Normal saline flushes have been used in previous case series of therapeutic thoracentesis in pleural infection. In addition, the PIT trial demonstrated that intrapleural flushes of 500ml three times a daily was effective at reducing the need for thoracic surgery (15). Within the ACTion cohort, intrapleural flushes of up to 500ml of sterile normal saline can be used twice daily (at the discretion of the treating physician), provided it is aspirated within the same pleural procedure or the chest tube is on continuous drainage to prevent accumulation of fluid. This will prevent catheter blockage and can assist in the clearance of infected pleural fluid from the pleural space.

Intrapleural fibrinolytics are used to breakdown septations that can develop within infected pleural fluid collections. Within the ACTion cohort they can be used, in either treatment arm, at the discretion of the treating physician. Within the control arm this will follow a well standardised local protocol. Within the intervention arm, if a patient is deemed to need fibrinolytics these can be administered via the therapeutic thoracentesis catheter or via a chest tube depending on the view of the treating physician.

In all trial patients, the use of intrapleural fibrinolytics should be considered in the following circumstances:

- Persistent or rising inflammatory markers (WBCs or CRP) or ongoing fevers despite 48hours of intravenous antibiotics and fluid drainage.
- Radiological evidence of ongoing fluid collection radiologically with no fluid output from the chest tube (control arm) and no clear site for further therapeutic thoracentesis (interventional arm)

The requirement for intrapleural fibrinolytics should be recorded as a trial outcome measure.

5.11. Referral for thoracic surgery

A referral to thoracic surgery is occasionally required to resolve pleural infection. This is often seen as an indicator of failure of medical management, so is important data to collect. The timing and indications for a referral is up to the treating physician.

The requirement for referral for surgery and surgical procedure performed will be recorded as a trial outcome measure.

5.12. Trial follow up visits

Trial follow up visits are exclusive of the “post procedure outpatients visits” documented above. Participants will be asked to return on days 30 (+/- 3days) and 90 (+/- 7days) after trial enrolment. At both these follow ups they will be asked to complete a HRQoL questionnaire with VAS.

At day 30 they may be asked to participate in a semi-structured interview (see below)

At day 90, as part of standard care, patients will have a clinical assessment, blood tests, chest radiograph, pleural ultrasound scan and pulmonary function tests. They will also be asked to complete the EQ-5D questionnaire. These data will be recorded on the trial database.

Patients who are unable to attend their trial follow up will be contacted by phone and as much trial data collected as is possible. Additionally, the EQ-5D questionnaire and VAS will be sent to them via post for completion and return to the trial co-ordinating centre.

Patients who are inpatients in North Bristol NHS Trust, at either Day 30 or 90, will be assessed whilst in hospital and have trial data collected as appropriate.

6. BIOLOGICAL SAMPLES, IMAGING, QUESTIONNAIRES AND INTERVIEWS

6.1. Biological samples

Blood

All of blood tests performed during the ACTion trial are part of the standard care of patients with pleural empyema. These samples will be processed at North Bristol NHS Trust via normal laboratory processes. There will be no requirement for storage of blood samples for research purposes.

These tests will include full blood count, urea and electrolytes, C-reactive protein, and liver function tests taken on at least alternate days for the first 7 days.

Pleural fluid

As part of the diagnosis of pleural empyema a diagnostic pleural aspiration is performed, which will, by definition, occur before enrolment in the ACTion trial. The results from this procedure will be recorded on the trial database and is expected to include pleural fluid protein, lactate dehydrogenase (LDH), glucose, pH, cytological assessment and standard microbiology (culture and microscopy). If any of the above standard pleural fluid investigations were not requested, they can be performed on this pleural fluid collected during therapeutic thoracentesis or chest tube insertion as per standard care. There will be no requirement for storage of pleural fluid for research purposes.

6.2. Imaging

Thoracic Ultrasound

All pleural ultrasounds will be performed as part of standard care. The scan results from the baseline assessment, third (+/- 1 day) and seventh (+/- 1 day) days should be recorded on the electronic trial database. Additionally, the results prior to any pleural procedure that are additional to the above should be recorded as they form part of the reasoning for additional pleural procedures. A pleural ultrasound should also be performed and recorded at the trial follow-ups (Day 30 and 90).

Scans should be performed by those with at least Royal College of Radiologists Level One accreditation (or equivalent).

Chest radiography

All chest radiographs performed during the ACTion trial are part of standard care. Images should ideally be performed as P-A. Whilst an inpatient, chest radiographs should be performed on Day 3 and Day 7, with additional as deemed necessary by the treating physician. They will also be performed after every pleural procedure as part of standard care (including chest tube removal), as well as on trial follow-ups (Day 30 and 90). Given the intervention arm may result in patients having additional pleural procedures there may be an increased number of chest radiographs required in this group. However, the exact number of additional pleural procedures is difficult to predict and forms part of the trial outcomes.

The size of effusion on chest radiograph will be reported by a clinical member of the research team and recorded in the online database.

6.3. Health related quality of life questionnaires

All patients will be asked to fill in an EQ-5D questionnaire and a VAS scoresheet for chest pain and breathlessness. These assessments will take place at baseline (Day 1), Day 3 (+/- 1 day), Day 7 (+/- 1 day) and at the trial follow ups (day 30 and 90).

EQ-5D

The EQ-5D is a 5 domain (paper-based or electronic) questionnaire which gives an overall assessment of an individual's quality of life at a particular timepoint. There are 5 questions and it is envisaged this should take between 1-2 minutes to complete.

VAS score

The ACTion trial is using a VAS score instrument to record patients reported chest pain and shortness of breath. The patient will be asked to mark on a line scale their assessment of their symptoms at that time. This should take around 30 seconds per scale.

6.4. Semi-Structured Interviews

An important aspect of a feasibility study is the participant experience of the trial processes, interventions and follow up. A selection of patient who were eligible for the ACTion trial (both those who accepted randomisation and those who did not) will be invited to semi-structured interviews. A

selection of healthcare professionals who were responsible for the clinical care of participants in the ACTion trial will be invited towards the end of the recruitment period.

Patient interviews

Patients will be given the interview specific PIS at the same time as they are given the ACTion trial specific PIS (near the time of diagnosis of their pleural infection). The interviews will take place 1 month after trial recruitment. This time period will ensure they are recovered from their condition without reducing recall.

Participants will be invited to have face-to-face or telephone interviews with [name]. The interview will be conducted at a time and place convenient for the patient (e.g. home, clinic or hospital). Interviewees will be asked to provide written informed consent prior to the interview commencing, including consent to be audio-recorded and for anonymised quotes to be used in the final report and any peer-reviewed literature.

Declining entry into the ACTion trial will not preclude a patient from being invited to interview, as the views of patients who declined randomisation will be particularly valuable.

The following interview topic guide was developed in collaboration with a pleural disease PPI group (26/10/17). The following areas were felt to be of significant importance;

- The patient experience of pleural infection.
- What were the participant's experiences of having a chest tube or thoracentesis.
- Experience and acceptability of the outpatient follow-up.
- Suggested improvements to trial processes or documents (consent, information sheet, etc).
- Reasons for declining participation in the trial (if applicable).

A sample size of 20 patient who were eligible for enrolment in the ACTion trial has been felt to be adequate to reach data saturation, such that no new data is emerging by the time of completion.

The final number interviewed may be different if the Sub-Investigator and qualitative supervisor ([name]) feel that data saturation has/hasn't been reached.

Healthcare professional interviews

Ten healthcare professionals who were significantly involved with the care of trial participants will be invited to interview near the end of the recruitment period. They will be provided with a specific PIS and given at least 24 hours to consider taking part. The consent process will be similar to the patient interviews with written informed consent required prior to the interview commencing, including consent to be audio-recorded and for anonymised quotes to be used in the final report and any peer-reviewed literature.

The interview topic guide will focus on the following areas

- The experience of using TT to manage pleural infection.
- Suggested improvements to the trial processes to optimise participant recruitment and retention.
- Understanding physician equipoise e.g. are there any patients with pleural infection that physicians would not be willing to randomise to a trial of this type?

As with the patient interviews the samples size (n=10) has been felt to be adequate to reach data saturation, such that no new data is emerging by the time of completion. The final number interviewed may be different if the Sub-Investigator and qualitative supervisor ([name]) feel that data saturation has/hasn't been reached.

All interviews

All interviews will be digitally audio-recorded, transcribed verbatim, and anonymised before being uploaded to NVivo data management software.

7. STATISTICAL ANALYSIS

7.1. Sample Size

As a feasibility study, sample sizes have not been formally calculated. The Pleural Irrigation Trial (PIT) was a single centre randomised pilot study based at Southmead hospital (before it merged with another large hospital in 2014). Over 2 years, 38 patients were recruited from 47 eligible patients with pleural infection (80% randomisation rate). This was achieved with more stringent inclusion criteria and a smaller medical take than the proposed trial. For this trial, we suggest that 30 patients randomised (15 in each arm) would be achievable given the timeframe (15 months). Internal audit over the last 4 months has identified 13 patients who would have been eligible for trial entry. Two patients identified by this audit have kindly agreed to act as members of a disease-specific PPI group for subsequent participation in the trial design and management.

This is an application for an extension to the current trial was made in January 2021 in order to maximise recruitment. Prior to the COVID-19 pandemic this trial was recruiting to time and target. The COVID-19 pandemic meant the trial closed for a period from March to June 2020. In addition, social distancing has significantly affected rates of invasive pneumococcal disease which is the main driver of rates of pneumococcal transmission. As a result, trial recruitment significantly slowed. An application to extend the duration of the trial by 12 months was granted (IF APPLICABLE) on xx.xx.xxxx.

7.2. Primary Outcome Analysis

Primary outcome is feasibility, specifically the acceptability of the trial intervention to patients. This will be assessed by proportion of the total number of patients who are eligible for trial entry that accept randomisation. The primary outcome will be defined as successful if $\geq 50\%$ of eligible patients are subsequently randomised.

7.3. Secondary Endpoint Analysis

Quantitative analysis will focus on obtaining estimates and measures of variation of key unknowns required for the design of a full-scale RCT of TT versus conventional chest tube in pleural infection. We need the following information in order to design an adequately powered trial;

- Descriptive statistics for rates of recruitment, randomisation, attrition, data completion (including differences between the intervention and controls).
- Descriptive statistics for the proposed secondary outcomes (including hospital LOS, number of procedures, readmission rates and surgical referrals), and common adverse clinical events (such as persistent fever, or abnormal blood chemistry and radiography).
- The costs of an ambulatory strategy will need assessing in monetary terms and data on social and NHS costs will be collected here and reviewed by health economic advisors as to their adequacy for use or to identify required amendments for a subsequent full trial.

7.4. Analysis of Semi-structured Interviews

Interview data will be analysed using Thematic Analysis. Audio-recordings will be listened to and transcripts read and re-read for familiarisation, then open coded to develop an initial code list. A subset of interviews will be independently double-coded by a member of the supervisory team with qualitative expertise ([name]) and code-lists compared, refined and re-applied to the dataset.

Codes will then be grouped into categories, and data explored to identify connections and to develop a descriptive account of the dataset. The analysis will focus on the acceptability of trial processes to patients and physicians, individual and group equipoise, and the patient experience of pleural infection and treatment.

7.5. Interim Analysis

No formal interim analysis for the primary outcome (feasibility) is planned. However, given this is the first randomised trial of this intervention in pleural infection, the Trial Steering Committee will be asked to review the trial's progress after ten patients have been successfully randomised in order to assess for safety and trial issues.

8. ADVERSE EVENTS

8.1. Definitions

Adverse Event (AE)

An untoward medical occurrence in a patient or clinical trial subject, administered the intervention and which does not necessarily have a causal relationship with this treatment.

Adverse Reaction

An untoward medical occurrence which has a clear causal relationship between the event and the research procedure.

Serious Adverse Event (SAE) / Serious Adverse Reaction (SAR)

Any untoward and unexpected medical occurrence or effect that:

- Results in death
- Is life-threatening – *refers to an event during which the subject was at risk of death at the time of the event; it does not refer to an event which hypothetically might have caused death if it were more severe*
- Requires hospitalisation, or prolongation of existing in-patients' hospitalisation
- Results in persistent or significant disability or incapacity
- Is or results in a congenital anomaly or birth defect

Medical judgement should be exercised in deciding whether an AE or AR is serious in other situations. Important AE/ARs which do not strictly meet the criteria for being serious but which may jeopardise the subject or require intervention to prevent one of the other outcomes listed in the definition above, should also be considered serious.

Suspected Unexpected Serious Adverse Reaction (SUSAR)

Any adverse event which is classed as serious and for which there is evidence of a causal relationship with a research procedure, but where that event is unexpected.

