8.5. Expected Adverse Events

The following are considered to be expected in the context of patients suffering with pleural infection and who require an intervention for fluid drainage.

- Chest pain, or discomfort around procedure site (unless not improving or remains unresponsive to analgesia)
- Bleeding associated with trial procedure (unless causing haemodynamic compromise, requiring transfusion, or requiring intervention to achieve haemostasis)
- Subcutaneous infection related to therapeutic thoracentesis or drain insertion, (unless unresponsive to antibiotic therapy)
- Chest drain falling out, becoming dislodged or becoming blocked
- Further pleural procedures required to drain ongoing fluid collection in either control or intervention group
- Pneumothorax or evidence of non-expandable lung following chest drain insertion or therapeutic thoracentesis (unless requiring surgical intervention)
- Hospital admission, elective procedure or surgery, disability, incapacity or death due to underlying or pre-existing condition
- Delay in planned discharge date (unless due to a complication directly related to a trial procedure)
- Readmission to hospital or need for thoracic surgery due to pleural infection or pneumonia
- Hypotension or tachycardia due to sepsis requiring intravenous fluid support alone
- Hypothermia or hyperthermia due to sepsis, within the range $\geq 34.0^{\circ}\text{C}$ to $\leq 39.4^{\circ}\text{C}$
- A reaction to an administered medication (unless not described in the current version of the British National Formulary (BNF))

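### Section 8.1 makes unexpectedness part of the SAE definition, so readmission and thoracic surgery for pleural infection, listed as expected in 8.5, fall outside 24-hour sponsor reporting

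*Protocol*

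**What the plan says.** Section 8.1 uses one definition for SAEs and SARs: "Any untoward and unexpected medical occurrence or effect that" meets one of five criteria. Two of these are "Results in death" and "Requires hospitalisation, or prolongation of existing in-patients' hospitalisation". A further clause asks for medical judgement on "Important AE/ARs which do not strictly meet the criteria for being serious but which may jeopardise the subject or require intervention". The SUSAR definition then takes an event that is already serious and causally related and adds "but where that event is unexpected".

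Section 8.5 says what counts as expected in this trial. The list includes "Readmission to hospital or need for thoracic surgery due to pleural infection or pneumonia", with no qualifier, and "Hospital admission, elective procedure or surgery, disability, incapacity or death due to underlying or pre-existing condition". It also includes delays in discharge, except those caused by a complication of a trial procedure.

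Section 8.2 requires SAEs and SARs to reach the sponsor within 24 hours of the investigator becoming aware of them. Other adverse events are recorded on the CRF, and the protocol anticipates that this will mostly happen at follow-up visits. Section 7.5 asks the Trial Steering Committee (TSC) to review progress after ten randomised patients "in order to assess for safety and trial issues".

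**The concern.** Seriousness describes the outcome of an event, and expectedness describes whether it was foreseen. Section 8.1 merges the two, so placing an event on the 8.5 list removes its serious status as well as its SUSAR status.

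The events affected are those by which failed drainage would show itself. Section 5.8 says that control patients will probably leave hospital only after resolution, whereas thoracentesis patients may leave before infection has fully cleared. Readmission and surgery for persisting infection are therefore foreseeable harms of the experimental strategy, and the gap may not fall equally on the two arms. Section 5.11 itself treats surgical referral as a sign that medical management has failed. At stake are how quickly the sponsor hears of such events and whether a count of SAEs by arm means what its readers will take it to mean.

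**Working it through.** No figure in the protocol needs reproducing. The check applies the 8.1 definition to the events listed in 8.5, and then follows the consequence through 8.2.

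| Event | Seriousness criterion (8.1) | Status in 8.5 | SAE as written? | Other capture |
|---|---|---|---|---|
| Readmission for pleural infection | Hospitalisation | Expected, unqualified | No | Secondary outcome, to 30 days (3.3) |
| Thoracic surgery for pleural infection | Hospitalisation or its prolongation | Expected, unqualified | No | Secondary outcome (3.3); recorded under 5.11 |
| Discharge delay not due to a procedure complication | Prolonged hospitalisation | Expected | No | Length of stay (3.3) |
| Death from an underlying or pre-existing condition | Death | Expected | No | All-cause mortality, days 30 and 90 (3.3) |
| Death from the index pleural infection | Death | Unclear | Unclear | Same |
| Any other unexpected death | Death | Not listed | Yes | Same |

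Step 1. The first four rows meet a seriousness criterion but fail the added condition, so they are not SAEs.

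Step 2. The 24-hour duty in 8.2 applies to SAEs and SARs. It therefore does not reach these rows, which need only a CRF entry. The scheduled trial visits are at days 30 and 90 (5.12), so an entry that waits for a visit could come well after the event.

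Step 3. If every SAE is already unexpected, the further condition in the SUSAR definition excludes nothing. Section 8.2 also names serious, related and unexpected as three separate tests for a SUSAR. Both places make sense only if seriousness does not already contain unexpectedness, so 8.1 does not fit the text around it.

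Step 4. SARs share the definition. Take a procedure-site infection that responds to antibiotics but leads to a hospital admission. It is procedure-related and meets the hospitalisation criterion, yet 8.5 lists it as expected. It is then neither a SAR nor a SUSAR, and no category is left for a serious, related, expected event.

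Step 5. The index-infection row cannot be settled from the text. Section 8.5 does not say whether the infection under treatment counts as an underlying condition, and the line on readmission and surgery does not mention death.

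**The case against.** The strongest reply is that nothing goes unrecorded. Readmission within 30 days, surgery, number of procedures and mortality are secondary outcomes (3.3), surgical referral is recorded under 5.11, 7.3 plans descriptive statistics, and every adverse event goes on the CRF. This stands: the loss is one of classification and speed. A reader might infer that these harms vanish from the trial, and the protocol does not support that.

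A reader might also infer that the TSC would face an empty SAE list at its ten-patient review. That is conjecture. Section 7.5 does not say what the TSC receives, the trial is unblinded (5.5) and single-site (9.6), and the management group's members sit on the TSC (11.2). They may well know of each event. What remains is that no section requires these outcomes to be shown by arm at that review.

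The judgement clause in 8.1 carries no condition of unexpectedness and can bring back individual cases. It is discretionary, however, and does not restore the listed events as a class.

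Finally, 8.5 never says that its events are exempt from SAE reporting, so 8.1 may simply be loosely drafted. That is plausible, but 8.5 is the protocol's list of what is expected, and staff who apply 8.1 as written would reach the exemption. If an exemption from expedited reporting is intended, no section says so.

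**Conclusion.** The point holds as an inconsistency between 8.1, 8.2 and 8.5. As written, readmission and thoracic surgery for pleural infection, most discharge delays and some deaths are not SAEs and carry no 24-hour duty. The conclusion rests on a literal reading in which the unexpectedness of 8.1 is judged against the 8.5 list.

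Its size cannot be given as an event count. The protocol states no readmission rate, and deaths, operations and readmissions can occur in the same patient, so adding their rates to reach a total of hidden events would be unsound. The protocol's own figures indicate only the scale:

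- Surgical referral at about 5% (2.1): 30 × 0.05 = 1.5 in the whole trial, and 10 × 0.05 = 0.5 among the first ten patients.
- Deaths, from 1.4% in low-risk patients (2.3) to about 5% in all cases (2.5): 30 × 0.014 = 0.4 to 30 × 0.05 = 1.5.

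These rates come from wider populations than a trial that excludes severe septation and sepsis needing more than basic fluids. Only part of the deaths would be affected, since 8.5 lists some deaths and not all. With numbers this small, one or two misclassified events could change the safety picture, so the wording should be corrected.

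**What to change.** 1. In 8.1, delete the words *and unexpected* from the SAE/SAR definition.
2. In 8.5, state that the list is used only to judge expectedness for SUSARs. If some serious events are meant to be exempt from expedited reporting, say so explicitly and name them.
3. In 8.5, say whether the index pleural infection counts as an underlying condition.
4. In 7.5, require deaths, readmissions and thoracic surgery by arm for the ten-patient review, whatever their expectedness. These data are already being collected.

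The cost is a protocol wording change, a few more SAE forms and one table for the TSC. No treatment, visit or outcome changes.
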